## 4 SELECTION AND ENROLLMENT OF SUBJECTS

The inclusion and exclusion criteria for the SUCCEED RCT are shown below:

**Table 3.** Inclusion and Exclusion Criteria of RCT

Inclusion Criteria

 
Patients of LAC + USC, Rancho Los Amigos, Olive View-UCLA, or Harbor-UCLA with onset of ischemic stroke, hemorrhagic stroke, or TIA within the prior three months.
 

Exclusion Criteria

 
Age < 40 years
 
SBP < 120 mm Hg
 
Speaks language other than English, Spanish, Korean, Mandarin, and Cantonese
 
Cannot provide informed consent due to dementia or aphasia
 

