- *Declining consent:* If patients do not consent to the study, the RA will record the reason why the patient did not consent. Further, the RA will ask permission to use the demographic information of the patient to generate enrollment propensity weights. Enrollment propensity weights will be used to analyze how the tendency to participate in the RCT impacts attainment of outcomes.
- *Storing consent forms.* The consent forms at each site will be stored in a locked file cabinet within a locked room. Access is limited to the site's Principal Investigator and research staff.

For the baseline survey, the RA will enter the circumstances of the initial visit (inpatient/outpatient, whether clinical team called RA or subject, reasons for ineligibility, and reasons for nonparticipation). These data will be summarized in a monthly report by site and shared among the Task Force and the research teams at UCLA and at each site.

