#### Screening, Entry Surveys, and Randomization

Screening for inclusion/exclusion criteria, baseline (entry surveys), and randomization occur in the same face-to-face encounter.

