#### 9.2.2 *Secondary outcomes*

Refer to **Table 1** provided below.

**Table 1.** Primary & Secondary Outcomes

Primary Outcome
Blood Pressure (change in blood pressure, as well as proportion of patients with BP under 120/80)
Secondary Outcomes
Risk of recurrent stroke, future cardiovascular event
Lipid profile: LDL cholesterol level, Triglyceride level, HDL cholesterol level
Hemoglobin A1c
C-reactive protein (CRP)
Adiposity: Body mass index (BMI), waist circumference, Waist-hip ratio, Waist-to-Height Ratio
Healthy Lifestyle Behaviors & Factors: Physical Activity, Diet, Smoking, Alcohol Use
Death

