### 9.3 Sample Size and Accrual

#### **Power Analysis**

Power Analyses was conducted with comparison of main outcomes (systolic blood pressure (SBP)) between the control and intervention arms. Based on availability of patients and our capacity, we plan to enroll 500 subjects from four senior centers. Using Intra-class correlation (ICC) of the four centers at 0.0085 level, attrition after the baseline between 20% to 30% level, mean SBP 141 mm Hg and standard deviation (SD) 20, three repeated measurements: baseline, 3 months, and 12 months (Brown and Prescott 2006), the underlying

statistical power of the study comes from two dimensions of observations: the number of unique subjects and the number of repeated measurements within a subject. Based on sample size and power analyses method proposed by Diggle et al. (1994) and Liu et al. (2005) for repeated measures analysis with a type I error of 0.05, type II error of 0.2 (or equivalent to power of 80%), 2.6 and 2.4 average data points for each subject (corresponding to 20% and 30% attrition respectively), and an auto-correlation at 0.2 level, the effective sample size will be 147 and 147 out of the planned 250 and 250 participants in each of the 2 arms (after adjusting for clustering effect), which will enable us to detect an effect size for SBP as small as 0.215 in standard deviation units or 4.29 mm Hg (for 20% attrition), and 0.253 in standard deviation units or 5.06 mm Hg (for 30% attrition).

The seminal work for moderator and mediator effect was from Baron and Kenny (1986). For potential moderators (e.g., age, gender, stroke type and severity, education, country of birth/primary language), we will test power of moderation using the most common measure of effect size  $f^2$  (Aiken & West, 2001), which equals the unique variance explained by the interaction term divided by sum of the error and interaction variances. Cohen (1988) has suggested that  $f^2$  effect sizes of 0.02, 0.15, and 0.35 are termed small, medium, and large, respectively. A more realistic standard for effect sizes with moderators might be 0.005, 0.01, and 0.025 for small, medium, and large, respectively.

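### The plan lets an unadjusted change in SBP be the primary result; committing to baseline SBP as a covariate would gain precision at no cost

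*Combined protocol and SAP*

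**What the plan says.** Table 1 in section 9.2 defines the primary outcome as "Blood Pressure (change in blood pressure, as well as proportion of patients with BP under 120/80". Neither measure is ranked above the other, and the row names no time point. The hypothesis under Primary Objective #2 (section 1.1) is an 8 mm greater SBP reduction than usual care at 1 year.

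Section 9.5 fits linear or ordinal logistic regressions, adjusted and unadjusted for covariates related to the outcome. It does not list those covariates, does not mention baseline SBP among them, and does not say which version is primary.

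The power analysis in 9.3 assumes "mean SBP 141 mm Hg and standard deviation (SD) 20", "three repeated measurements: baseline, 3 months, and 12 months" and "an auto-correlation at 0.2 level". It is set up "for repeated measures analysis with a type I error of 0.05, type II error of 0.2 (or equivalent to power of 80"%, and it contains no variance for a change score.

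On the baseline itself, section 6.2.1 states: "Screening for inclusion/exclusion criteria, baseline (entry surveys), and randomization occur in the same face-to-face encounter". Table 3 admits patients "with onset of ischemic stroke, hemorrhagic stroke, or TIA within the prior three months", and section 4.3.3 allows for enrolment in a hospital room. Section 6.3.7 averages two readings per occasion, with two more taken if the first two differ by more than 5 mm Hg.

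**The concern.** Change from baseline is a natural reading of both Table 1 and the hypothesis. Section 9.5 permits that change to be compared between arms with nothing else in the model. When two readings on the same person are only weakly correlated, subtracting the first adds its noise to the second. The plan's own correlation is weak. A baseline taken anywhere from the admission to three months after onset also gives no reason to expect a strong one.

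At stake is how much of the trial's information reaches the primary estimate. The same data, analysed with baseline SBP as a covariate, would give a narrower interval. Leaving the choice open also means that two models with different precision both qualify as the primary analysis.

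**Working it through.** **Inputs.** From 9.3: SD 20, mean 141, auto-correlation 0.2, alpha 0.05, power 80%, attrition 20% to 30% of 250 per arm, effective n of 147 per arm. From 1.1: 8 mm Hg.

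**Assumptions.** The test is two-sided (sidedness is not stated), the SD is the same at both times, and 0.2 is the baseline-to-12-month correlation rho (its structure is not stated). The contrast is at 12 months, without the enrolment and attrition weights.

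**The plan's own figure.** For a time-averaged difference with m readings per subject, d = 2.802 × sqrt(2[1 + (m − 1)rho] / (m n)).
- n = 147, m = 2.6: 2.802 × sqrt(2 × 1.32 / 382.2) = 0.233 SD = 4.66 mm Hg. The plan prints 4.29.
- n = 147, m = 2.4: 2.802 × sqrt(2 × 1.28 / 352.8) = 0.239 SD = 4.77 mm Hg. The plan prints 5.06.

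The printed pair is not reproduced. The comparison below does not depend on it; it uses only the SD, the correlation and the sample sizes.

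**Variance per subject.**
- Unadjusted change: 2 × SD² × (1 − rho) = 2 × 400 × 0.8 = 640, SD 25.3.
- 12-month SBP, ignoring baseline: SD² = 400, SD 20.0.
- Adjusted for baseline: SD² × (1 − rho²) = 400 × 0.96 = 384, SD 19.6.

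Change against adjusted: 640 / 384 = 1.67. In general the ratio is 2(1 − rho) / (1 − rho²) = 2 / (1 + rho).

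| rho | Change / adjusted | Change / 12-month SBP alone |
|---|---|---|
| 0.2 | 1.67 | 1.60 |
| 0.5 | 1.33 | 1.00 |
| 0.7 | 1.18 | 0.60 |

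If 0.2 is instead the correlation between adjacent visits and decays, baseline to 12 months could be 0.2² = 0.04, and the first ratio becomes 2 / 1.04 = 1.92.

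**Detectable difference** at rho 0.2: 2.802 × SD × sqrt(2 / n). The first two rows are 250 per arm less 20% and 30%, with no clustering. The last takes the plan's 147 as printed, which already carries its own clustering adjustment.

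| n per arm | Change | Adjusted | Power for 8 mm Hg: change | Adjusted |
|---|---|---|---|---|
| 200 | 7.1 | 5.5 | 89% | 98% |
| 175 | 7.6 | 5.9 | 84% | 97% |
| 147 | 8.3 | 6.4 | 77% | 94% |

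**Selection on SBP.** Assume N(141, 20) describes patients before selection and only readings of 120 or above are kept, the direction given in Table 3 and 4.2.6. (Section 4.2.2 prints the opposite direction, and these must be reconciled.) The baseline then has mean 146.4 and SD 16.1, variance about 258. Change variance is 0.8² × 258 + 384 = 549, and 549 / 384 = 1.43. Both arms would fall by 0.8 × (146.4 − 141) = 4.3 mm Hg without any treatment effect.

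**The case against.** The strongest reply is that a change outcome need not be analysed unadjusted. Section 9.5 includes adjusted models. Baseline SBP would correlate with change at −sqrt((1 − 0.2) / 2) = −0.63, so it fits the plan's description of a covariate. Once it is in the model, change and 12-month SBP give the same treatment estimate. The power section also assumes a repeated-measures analysis, not a change score. All of this is right, and it means the loss applies only to the least favourable analysis that 9.5 allows. It does not remove the point, because nothing makes the adjusted model primary.

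A second reply is that even the unadjusted score has 84% to 89% power for 8 mm Hg at 175 to 200 per arm. That also stands. The shortfall below 80% appears only at the plan's effective 147.

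Several stronger readings are tempting, and the documents do not support them:

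- *Change is less precise than ignoring baseline.* This holds at 0.2 but reverses above 0.5, and 0.2 is a planning value of unstated structure.
- *Change is the sole primary outcome.* It is one of two unranked measures.
- *The eligibility reading is the baseline reading.* The single encounter in 6.2.1 and the single screening/baseline column in 6.1 make this likely, but no section says so. Each occasion is also an average of readings.
- *Selection at 120 biases the result.* Baseline precedes randomization, so regression to the mean affects both arms alike and cancels in the contrast.
- *Chance baseline imbalance is an extra harm.* It is already counted in the change-score variance.

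**Conclusion.** The point holds as a loss of precision that the plan permits and could avoid. At SD 20 and a correlation of 0.2, an unadjusted change score carries 67% more variance than the baseline-adjusted analysis. Under the selection assumption above the figure is about 43%. It shrinks to 33% at a correlation of 0.5 and 18% at 0.7, but never changes sign: under equal SDs, 2 / (1 + rho) exceeds 1 for every correlation below 1. The recommendation therefore does not depend on the value 0.2, although the size of the gain does. The treatment estimate is not biased under either analysis.

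**What to change.** In 9.2 and 9.5, state that the primary analysis of the continuous measure is the between-arm difference in 12-month SBP, from a linear regression adjusted for baseline SBP and the stratification factors (site, language, stroke type). Report the unadjusted change as descriptive or as a sensitivity analysis only.

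Enrolment setting could be an optional further covariate, since section 4.3.3 has it recorded: "the RA will enter the circumstances of the initial visit (inpatient/outpatient". Days from stroke onset should be added only if the onset date is recorded; section 4.3.3 says that onset is asked about to confirm eligibility, not that the date is kept.

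The cost is a few sentences, to be settled before outcomes are seen by arm. Baseline SBP and the stratification factors are already collected. The change does not settle how the proportion under 120/80 ranks against the continuous measure, which needs its own statement.

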### 9.3 Sample Size and Accrual

#### **Power Analysis**

Power Analyses was conducted with comparison of main outcomes (systolic blood pressure (SBP)) between the control and intervention arms. Based on availability of patients and our capacity, we plan to enroll 500 subjects from four senior centers. Using Intra-class correlation (ICC) of the four centers at 0.0085 level, attrition after the baseline between 20% to 30% level, mean SBP 141 mm Hg and standard deviation (SD) 20, three repeated measurements: baseline, 3 months, and 12 months (Brown and Prescott 2006), the underlying

statistical power of the study comes from two dimensions of observations: the number of unique subjects and the number of repeated measurements within a subject. Based on sample size and power analyses method proposed by Diggle et al. (1994) and Liu et al. (2005) for repeated measures analysis with a type I error of 0.05, type II error of 0.2 (or equivalent to power of 80%), 2.6 and 2.4 average data points for each subject (corresponding to 20% and 30% attrition respectively), and an auto-correlation at 0.2 level, the effective sample size will be 147 and 147 out of the planned 250 and 250 participants in each of the 2 arms (after adjusting for clustering effect), which will enable us to detect an effect size for SBP as small as 0.215 in standard deviation units or 4.29 mm Hg (for 20% attrition), and 0.253 in standard deviation units or 5.06 mm Hg (for 30% attrition).

The seminal work for moderator and mediator effect was from Baron and Kenny (1986). For potential moderators (e.g., age, gender, stroke type and severity, education, country of birth/primary language), we will test power of moderation using the most common measure of effect size  $f^2$  (Aiken & West, 2001), which equals the unique variance explained by the interaction term divided by sum of the error and interaction variances. Cohen (1988) has suggested that  $f^2$  effect sizes of 0.02, 0.15, and 0.35 are termed small, medium, and large, respectively. A more realistic standard for effect sizes with moderators might be 0.005, 0.01, and 0.025 for small, medium, and large, respectively.

Due to the low power in tests of moderation, there are greater interests in mediation over moderation (McClelland & Judd, 1993). To analyze power of potential mediators (e.g., self-efficacy, self-management, social isolation, depression, perceived risk of stroke), we will use indirect effect, which is the product of coefficient from independent variable to mediator, and mediator to the outcome. Because an indirect effect is a product of two effects, the usual Cohen (1988) standards of .1 for small, .3 for medium, and .5 values should be squared. Thus, a small effect size would be .01, medium would .09, and large would be .25 (or we can use small .02, medium .15, and large .40.)

The effect size for SBP as small as 0.215 in standard deviation units or 4.29 mm Hg (for 20% attrition), and 0.253 in standard deviation units or 5.06 mm Hg (for 30% attrition) can be considered clinically meaningful in the present of both moderators and mediators. Thus, the planned sample size should be sufficient for analyses.

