**Primary Objective #2:** To test the impact of a sustainable Chronic Care Model-based intervention on control of systolic blood pressure (primary outcome), composite stroke risk, and each individual stroke risk factor (secondary outcomes), among 500 adults (over 90% minority) recruited “early” - during or shortly after hospitalization for an ischemic or hemorrhagic stroke or TIA - at one of the four Los Angeles County safety net medical centers. We will conduct a randomized trial of this intervention that includes the new, community-centered component developed in aim #1, and a “re-engineered” healthcare delivery system with nurse practitioners or physician assistants as care managers, distribution of home blood pressure monitors, group clinics, and a care management software system tailored to secondary stroke prevention and interfaced with the mobile health platform used by the CHWs, relative to usual care. We will include non-English speaking individuals from Hispanic, Chinese, and Korean racial and ethnic groups, and a broad range of stroke severity. We will analyze potential moderators (age, gender, stroke type and severity, education, country of birth/primary language, diabetes comorbidity, care team composition) to understand robustness of intervention impacts across levels of individual and health system characteristics. We will conduct a formative evaluation to continuously improve implementation, and will measure and analyze extent of intervention implementation, as it is delivered for up to 12 months after stroke or TIA through transition of patients into primary care. We will analyze potential mediators (life chaos, competing needs, medication adherence, knowledge of stroke risk factors, participation in self-management programs, social isolation, depression, health literacy, engagement with healthcare provider team, attitudes/health beliefs, self-efficacy, readiness to change, perceived risk, and perceptions of quality of interactions with provider) of the intervention’s impact, using both qualitative and quantitative methods.

*Hypothesis: Patients randomized to the SUCCEED intervention will achieve 8mm greater reduction in systolic blood pressure reduction and lower stroke risk scores at 1 year versus those randomized to usual care.*

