#### 4.3.4 *Procedure for obtaining intervention group assignment*

Before the RCT begins, we will use computer-assisted stratified randomization of block size of 4. The three stratification variables will be site, spoken language (Spanish, English or other), and type of stroke (ischemic or hemorrhagic). These lists have an allocation ratio of 1:1 of control and intervention. Permuted block randomization that stratifies by site will be used to promote periodic balance through the trial and group balance at the end of the trial. The study programmer/analyst will generate 24 lists, one for each stratum. Each row of the list will include a unique subject IDs and intervention arm of the study. The lists will be kept in a notebook that the Project Coordinator will possess at all times.

For patients who consent to the study and meet inclusion criteria, the RA will collect baseline data (described below in section of Outcome Measures) before randomization so that the RA will collect data uniformly regardless of the eventual allocation of the subject. After an eligible participant has consented and completed the baseline survey, the RA will inform the Project Coordinator with the information needed to choose which of the 24 lists to use. The Project Coordinator will find the next uncrossed row, tell the RA the unique subject ID and intervention assignment, then cross out that row so that the next row will be used when this list is used again.

The Project Coordinator will assign the newly enrolled participant a unique subject ID and inform the RA the assigned randomization status of this subject. The Project Coordinator will mark down in the notebook the date of randomization for that subject ID.

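### The power calculation in section 9.3 counts the pre-randomisation baseline SBP as an outcome observation, so the printed 4.29 mm Hg is not a detectable post-randomisation difference

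*Combined protocol and SAP*

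**What the plan says.** Section 9.3 (Power Analysis) takes "mean SBP 141 mm Hg and standard deviation (SD) 20", a site intraclass correlation of 0.0085, a within-subject correlation of 0.2, type I error 0.05 and 80% power. It plans on "three repeated measurements: baseline, 3 months, and 12 months", with "attrition after the baseline between 20% to 30% level", and says that power comes from "the number of unique subjects and the number of repeated measurements within a subject". The average count per person is given as "2.6 and 2.4 average data points for each subject (corresponding to 20% and 30% attrition respectively". From an effective 147 of 250 per arm, it prints detectable differences of 0.215 SD (4.29 mm Hg) at 20% attrition and 0.253 SD (5.06 mm Hg) at 30%. The last paragraph of 9.3 calls these clinically meaningful and concludes that the sample size is adequate.

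Other sections bear on the point:

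- Section 4.3.4: "the RA will collect baseline data (described below in section of Outcome Measures) before randomization". Section 6.2.1 adds that these evaluations precede any study intervention.
- Section 1.1, Primary Objective #2: "Patients randomized to the SUCCEED intervention will achieve 8mm greater reduction in systolic blood pressure reduction", assessed at 1 year.
- Section 9.2, Table 1: the primary outcome is change in blood pressure, together with the proportion below 120/80.
- Section 9.5: linear or ordinal logistic regression with participation weights. It names neither a repeated-measures model nor a role for baseline SBP.

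**The concern.** A formula for the average arm difference over several visits assumes that the same difference is present at each visit. At baseline the expected difference is zero, because subjects have not yet been randomised or treated. Counting that visit shrinks the variance of the average as if a further informative reading had been taken, while the average effect itself is pulled towards zero. The printed result then looks like a smaller detectable treatment effect than the follow-up data can support.

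At stake is the accuracy of the only power statement for the primary outcome, and of the sentence in 9.3 that relies on it to call the sample size sufficient.

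**Working it through.** **Inputs from section 9.3:** n = 147 effective per arm, SD = 20, correlation 0.2, alpha 0.05, power 80%, attrition 20% or 30%. Sidedness and correlation structure are not stated. Two-sided alpha and first-order autoregressive, AR(1), correlation are inferred because together they reproduce both printed figures.

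**Step 1. The data-point counts.** 1 + 2 × 0.8 = 2.6 and 1 + 2 × 0.7 = 2.4. The leading 1 is baseline, always observed. The other two terms are the follow-up visits after attrition.

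**Step 2. Reproducing the printed differences.** For a mean of m readings with relative variance V:

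detectable difference = (1.960 + 0.8416) × 20 × √(2V/147)

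- m = 3, AR(1): V = (3 + 4 × 0.2 + 2 × 0.04)/9 = 3.88/9 = 0.431. Result 0.2146 SD = **4.29 mm Hg**, as printed.
- m = 2: V = (2 + 2 × 0.2)/4 = 0.60. Result 0.2531 SD = **5.06 mm Hg**, as printed.

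So 2.6 and 2.4 appear to have been rounded to 3 and 2. Compound symmetry with m = 2.6 and 2.4 gives 4.66 and 4.77, and with m = 3 gives 4.47. One-sided alpha also fails, giving 3.81 to 4.49 for m = 3 to 2. Section 9.3 lists only two readings after baseline, so 4.29 needs baseline as its third. The 5.06 figure could be baseline plus one follow-up, which fits the 2.4 count, or two complete follow-ups.

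**Step 3. Follow-up readings only, n = 147.**

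- Both visits complete (m = 2): 5.06 mm Hg. This is the like-for-like effect of removing baseline from the three-reading average: 5.06/4.29 = 1.18. Power for 4.29 mm Hg is 66%.
- For fractional counts I assume compound symmetry, V = (1 + (k − 1) × 0.2)/k:

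| Attrition | k | V | Detectable difference | Printed | Power for printed value | Power for 8 mm Hg |
|---|---|---|---|---|---|---|
| 20% | 1.6 | 0.700 | 5.47 mm Hg | 4.29 mm Hg | 59% | 98% |
| 30% | 1.4 | 0.771 | 5.74 mm Hg | 5.06 mm Hg | 70% | 97% |

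Power is Φ(d / (20 × √(2V/147)) − 1.96), where d is the true difference. For example, 4.29/1.952 − 1.96 = 0.24, which gives 59%.

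**Step 4. The 12-month comparison alone.** Section 1.1 states the 8 mm Hg hypothesis at 1 year. Applying attrition to 147 leaves 117.6 or 102.9 per arm. The unadjusted detectable difference, 2.8016 × 20 × √(2/n), is 7.31 or 7.81 mm Hg. Power for 8 mm Hg is 87% or 82%.

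**Step 5. Two inputs carried over unverified.**

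- *Effective n.* 250/(1 + (250/3 − 1) × 0.0085) = 147.1, which uses three sites. Section 9.3 says four; section 9.5 mentions three in one place. Four sites give 164 (62.5 per site per arm) or 122 (125 per site). The Step 3 differences become 5.18 and 5.44 mm Hg, or 6.01 and 6.31 mm Hg.
- *Number of readings.* The schedule in 6.1 marks the physical examination, including blood pressure, at 8 months. The Synopsis lists examinations only at baseline, 3 and 12 months.

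**The case against.** The strongest defence is that baseline is a legitimate part of a longitudinal analysis. A model may keep it as a response, with the treatment effect defined at follow-up, so its presence in the list is not itself an error. That is right, and the fix allows for it. But the printed 4.29 mm Hg does not come from such a model. It comes from a plain average over three readings, and no section gives baseline another role in the power calculation.

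A second objection is that 5.47 and 5.74 mm Hg use a different formula from the plan's, so setting them against 4.29 and 5.06 mixes the baseline problem with a change of method. This stands in part. Within compound symmetry the comparison is 4.66 to 5.47 and 4.77 to 5.74, increases of 17% and 20%. Within the plan's apparent AR(1) method it is 4.29 to 5.06, or 18%. The direction and approximate size hold either way. It also stands that 5.06 equals the figure for two complete follow-up visits, so dilution of that number is not proven.

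A reader might go further and infer that the true detectable difference at 30% attrition exceeds the hypothesised 8 mm Hg, for instance by doubling 5.06 to 10.1 on the view that baseline is one of two averaged readings. The documents do not support this. It needs an analysis that averages baseline into the outcome, and none is planned: Table 1 names change, section 1.1 refers to 1 year, and section 9.5 plans regression. Once only follow-up readings are counted, the follow-up average has a detectable difference well below 8 mm Hg.

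Finally, section 9.3 sets the 500 by patient availability and capacity, not by these differences. That limits the consequence but does not make the figures right.

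**Conclusion.** Wrong as written; it should be fixed. The calculation counts as outcome data a reading that cannot carry a treatment effect. The 4.29 mm Hg is firmly affected; for 5.06 mm Hg the effect depends on which two readings were used. On follow-up readings only, the detectable difference is about 5.1 mm Hg with complete data and 5.5 to 5.7 mm Hg with the plan's attrition. The last range is 27% and 13% above the printed values.

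The error alone does not make the trial underpowered for 8 mm Hg. The margin is narrower for the 12-month comparison, at 7.3 to 7.8 mm Hg unadjusted.

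These results assume two-sided alpha, the plan's SD of 20, correlation of 0.2 and 147 per arm, two follow-up readings, and compound symmetry for fractional counts.

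**What to change.** In section 9.3, including its closing paragraph:

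1. Base the detectable differences on post-randomisation SBP readings only. Use baseline as a covariate, or as a response constrained to have no arm difference.
2. Replace the 2.6 and 2.4 counts and the 4.29 and 5.06 mm Hg figures with recalculated values. State the sidedness, the correlation structure, how attrition enters, and whether the target is the follow-up average or the 12-month difference.
3. Before recalculating, confirm the effective 147 per arm against the number of sites, and reconcile section 6.1 with the Synopsis on whether blood pressure is measured at 8 months.
4. Reword the adequacy conclusion to rest on the new figures and the 8 mm Hg hypothesis.

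The cost is a recalculation and a text edit. Correcting the baseline count requires no change to recruitment, visits or treatment.

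### The detectable SBP differences in Section 9.3 (4.29 and 5.06 mm Hg) do not follow from the inputs printed beside them, and no figure is given for the 1-year comparison

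*Combined protocol and SAP*

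**What the plan says.** Section 9.3 describes a calculation "for repeated measures analysis with a type I error of 0.05" and 80% power, with SD 20 mm Hg. It uses "three repeated measurements: baseline, 3 months, and 12 months", and "attrition after the baseline between 20% to 30% level". These become "2.6 and 2.4 average data points for each subject (corresponding to 20% and 30% attrition respectively), and an auto-correlation at 0.2 level".

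The clustering input is stated as "Using Intra-class correlation (ICC) of the four centers at 0.0085 level". After that adjustment, "the effective sample size will be 147 and 147 out of the planned 250 and 250 participants in each of the 2 arms". The results are 0.215 SD (4.29 mm Hg) at 20% attrition and 0.253 SD (5.06 mm Hg) at 30%.

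The end of Section 9.3 repeats the figures ("The effect size for SBP as small as 0.215 in standard deviation units or 4.29 mm Hg (for 20% attrition", and likewise the 30% figure) and closes: "Thus, the planned sample size should be sufficient for analyses".

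Elsewhere, Section 1.1 (Primary Objective #2) hypothesises an 8 mm greater SBP reduction at 1 year. Table 1 in Section 9.2 names change in blood pressure, together with a proportion below 120/80, as primary. Section 9.5 plans weighted ordinal logistic or linear regression, with and without covariates, and does not name one primary SBP model.

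**The concern.** The two printed differences share the same sample size, SD, type I error, power and correlation. Only the average number of measurements changes, from 2.6 to 2.4. So small a change should barely move the result, yet the printed figure rises by 18%.

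Two further features are hard to reconcile with the text. The 147 should follow from the ICC and four centers. And with attrition counted only after baseline, 2.6 and 2.4 appear to treat the baseline reading as an outcome, although Sections 4.3.4 and 6.2.1 place it before randomisation and before any intervention, so it carries no treatment effect.

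At stake is whether the sufficiency statement has a basis that a reader can reproduce, and whether it concerns the comparison by which the 8 mm Hg hypothesis will be judged.

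**Working it through.** **Inputs (Section 9.3).** SD 20; type I error 0.05, two-sided assumed because sidedness is not stated; power 80%; n = 147 per arm; correlation ρ = 0.2; m = 2.6 or 2.4 measurements. The multiplier is 1.960 + 0.842 = 2.802.

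**Formula.** For a comparison of time-averaged means, d = 20 × 2.802 × √(2f/n), where f is the variance of the mean of m correlated measurements relative to a single one.

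- Exchangeable correlation: f = [1 + (m − 1)ρ]/m.
- AR(1): f = (1/m)[(1 + ρ)/(1 − ρ) − 2ρ(1 − ρ^m)/(m(1 − ρ)²)].

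**Reproducing the plan's figures.** Both come out under AR(1) with whole numbers of measurements:

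- m = 3: f = 0.4311, d = 4.29 mm Hg.
- m = 2: f = 0.6000, d = 5.06 mm Hg.

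**Using the stated 2.6 and 2.4.**

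| | m = 2.6 (20%) | m = 2.4 (30%) |
|---|---|---|
| AR(1) | f = 0.4859, d = 4.56 | f = 0.5188, d = 4.71 |
| Exchangeable | f = 0.5077, d = 4.66 | f = 0.5333, d = 4.77 |
| Power at the printed value | 73–75% at 4.29 | 84–85% at 5.06 |

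Modelling dropout as a mix of people with three measurements and people with baseline only gives the same AR(1) answers: f = 1/(0.8/0.4311 + 0.2) = 0.486, d = 4.56; and f = 1/(0.7/0.4311 + 0.3) = 0.520, d = 4.71.

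**Ratio check, free of n, SD and sidedness.** Printed: 5.06/4.29 = 1.18. Expected from 2.6 to 2.4: √(0.5188/0.4859) = 1.033 under AR(1), or √(0.5333/0.5077) = 1.025 exchangeable. From 3 to 2 under AR(1): √(0.6/0.4311) = 1.18. A one-sided test (multiplier 2.486) gives 4.04–4.13 and 4.18–4.24, matching neither printed value.

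**The 147.** Effective n = 250/[1 + (k − 1) × 0.0085] for clusters of size k.

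- k = 62.5 (four sites, within arm): 250/1.523 = 164.
- k = 125 (four sites, both arms): 250/2.054 = 122.
- Solving 250/147 = 1.70 for k gives about 83, that is 250/3 or 500/6.

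**Baseline as outcome.** 1 + 0.8 + 0.8 = 2.6 and 1 + 0.7 + 0.7 = 2.4, so baseline is the leading 1.

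**12-month comparison.** Completers per arm: 250 × 0.8 = 200 and 250 × 0.7 = 175. The baseline-to-12-month correlation r is not given, so it is ranged as an assumption. The formula for d is as above with n = 200 or 175, and f = 1 − r² (baseline-adjusted) or 2(1 − r) (change score). There is no allowance for clustering or weighting. Entries are for 20%/30% attrition.

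| r | Adjusted, mm Hg | Power for 8 | Change score, mm Hg | Power for 8 |
|---|---|---|---|---|
| 0.04 | 5.6/6.0 | 98/96% | 7.8/8.3 | 82/77% |
| 0.2 | 5.5/5.9 | 98/97% | 7.1/7.6 | 88.5/84% |
| 0.5 | 4.85/5.2 | 99.6/99% | 5.6/6.0 | 98/96% |

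**The case against.** The strongest reply is that the conclusion survives. Three and two may simply be 2.6 and 2.4 rounded to whole visits. The restated figures stay well below 8 mm Hg, and Section 9.3 sets enrolment by patient availability and capacity, not by 4.29 or 5.06. All of that stands. Rounding is a plausible inference, but the text does not disclose it, and it labels a no-attrition result as the 20% case.

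A second reply is that calling 4.29 too optimistic depends on keeping 147, which is itself in doubt. This also stands. With 164 per arm, AR(1) at 2.6 measurements gives 4.31, almost the printed value (though 2.4 gives 4.45, not 5.06). With 122 the figures are 5.01 and 5.17; with all 250, 3.49 and 3.61. Allocation is 1:1 within site strata (Sections 4.3.4 and 9.1) and site dummies are planned (Section 9.5), so a full site design effect on the arm comparison is probably conservative. The mismatch with the printed inputs is established; the direction of error for the actual design is not.

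A reader might go further and infer that the trial is underpowered. An unadjusted change score combined with the 250/147 = 1.70 deduction gives power for 8 mm Hg of 60/54%, 68/62% and 87/82% at correlations 0.04, 0.2 and 0.5. The documents do not support that inference: they do not commit to an unadjusted change score, they do not give the correlation, and the deduction is the very quantity that cannot be derived.

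Two other inferences go too far. That 147 reflects three clusters is only a guess, although Section 9.5 does mention both four hospital systems and three sites. That 5.06 counts baseline as an outcome is not shown either, since two measurements could be the two post-baseline visits.

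**Conclusion.** The plan is wrong as written, in a limited way. The ratio of the two differences proves the inconsistency whatever the sidedness or sample size, and both values are matched to the printed digit by three and two measurements under AR(1). If the stated 147, 2.6 and 2.4 are kept and the test is two-sided, 4.29 is about 0.3 to 0.4 mm Hg too small and 5.06 about 0.3 too large. The 147 is not derivable from four centers at the stated ICC.

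The more consequential gap is that the sufficiency statement concerns an average over visits that includes baseline, while the hypothesis concerns 1 year. Without clustering or weighting, a baseline-adjusted 12-month analysis would have at least 96% power for 8 mm Hg over the correlations examined, and a change score 77% to 98%. The answer therefore turns on a model and a correlation that the plan does not state. This should be fixed, but it is not evidence that the trial is too small.

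**What to change.** - In Section 9.3, at both places where they appear, replace 4.29 and 5.06 with values that follow from the stated inputs: about 4.6–4.7 and 4.7–4.8 mm Hg if 147 and 2.6/2.4 are kept. State the sidedness and the correlation structure.
- Correct 147, or state the number and size of clusters behind it and why a site design effect applies when allocation is balanced within site.
- Name the primary SBP model in Section 9.5; the choice is the team's. Add to Section 9.3 the detectable 12-month difference and the power for 8 mm Hg under that model. Count only post-baseline SBP as outcome, and show the assumed baseline-to-12-month correlation as a range. The last table under the working supplies figures for two candidate models; a repeated-measures model would need its own 12-month figure.
- Say that the enrolment and attrition weights in Section 9.5 would lower power. No particular weighting design effect need be printed.

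The cost is one rewritten paragraph, its repeat at the end of Section 9.3, and a commitment to one model in advance. No change in enrolment is proposed.
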